### **Behavioral Outcomes**

**Daily Physical Activity:** Student, peer mentor, and teacher participants will wear [accelerometers](#) for 7 straight days (1 week) of physical activity data collection measures for each data collection cycle (described above). The data will be used to estimate time spent in sedentary, moderate, and vigorous activity. Readings at or above 3962 counts per minute will be treated as vigorous physical activity. Moderate physical activity cut points are between 1535-3961 counts per minute. Readings between 100-1534 counts per minute are light activity. Readings less than 100 counts per minute will be treated as sedentary activity. Two or more hours of zero counts suggests that device as not worn and will be excluded from sedentary analysis.

**Healthy Lifestyle Behaviors Scale:** Student and peer mentor participants will respond to 8 items on a 5-point Likert scale. Face and content validity are established for physical activity and sedentary behaviors (8 items) when used with teens. Internal consistency reliability has been reported at  $\alpha = .78$  when used with teens.

**Daily Lifestyle Patterns:** A 4-item questionnaire will be given to ask participants to estimate their daily SSB consumption, water consumption, and hours of sleep per day during the past 4 weeks. Internal consistency reliability has been reported ( $\alpha > .80$ ) when used with teens residing in rural Appalachia ([name] & Holloman, 2014). .

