In adherence to school and district policies, teacher participants will not be provided any financial incentive for their participation.

Informed consent will be documented on a participant tracking form. This form allows linkage of the participant to their study identification number. For subsequent data collection, the identification number will be used instead of any identifiable information. All databases will be encrypted and password-protected. We will use a registration and tracking number that is randomly generated to document all measurement activities within individuals. Once informed consent is given, information on physical activity levels will be collected using the Actical accelerometer. Collection of the physical activity variable requires that the Actical be worn by the study participant for seven study days, and requires two school visits by the measurement team for each participant. Participants will be informed of the procedure used to wear the Actical monitor as outlined in the Actical user manual. There will be a demonstration of the correct right iliac crest placement of the monitor using a belt provided by the study. Each subject will receive a belt that allows for the correct placement of the monitor and written directions for the subject and parent to assure correct placement of the device in subsequent days. The subject will receive a reminder daily from their classroom teacher during the monitoring period to make sure that they are wearing the monitor and to answer any questions they may have. After seven days of monitoring, the measurement team will return to the school collect the devices, debrief the participant, and provide an incentive. Actical monitor data will be downloaded to a laptop PC at the school site by the measurement team. This requires the use of the download device and software provided by the vendor. The monitor will then be reset and redistributed for use by another

subject in that school. This process will be repeated weekly for three weeks at each school, representing three waves of data collection in a different one-third of the participating students each week.

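### Sedentary time from the accelerometer has no sleep or waking-hours rule, so sleep in the monitor broken by small movements counts as sedentary while still stretches and nights without the monitor are excluded

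*Combined protocol and SAP*

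**What the plan says.** In section IV, under Behavioral Outcomes (Daily Physical Activity), the protocol names the quantities it wants from the monitor: "The data will be used to estimate time spent in sedentary, moderate, and vigorous activity". The sedentary cut point is "Readings less than 100 counts per minute will be treated as sedentary activity". The sentence after it gives the only exclusion: "Two or more hours of zero counts suggests that device as not worn and will be excluded from sedentary analysis".

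The same paragraph asks for seven consecutive days of wear in each data collection cycle. Section B (Detailed Study Procedures) repeats that the measure "requires that the Actical be worn by the study participant for seven study days". On how to wear the device, section B says "Participants will be informed of the procedure used to wear the Actical monitor as outlined in the Actical user manual", and it promises "written directions for the subject and parent to assure correct placement of the device in subsequent days". It also provides for a daily reminder from the classroom teacher.

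None of this text says whether the monitor stays on at night, limits scoring to waking hours, or identifies sleep. Table 1 lists the accelerometer measure only as seven days of daily activity. Sleep is recorded separately, as self-reported hours over the past four weeks in the Daily Lifestyle Patterns questionnaire, and nothing links that answer to accelerometer scoring.

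**The concern.** Sedentary time is meant to describe waking behaviour, but sleep also produces counts below 100 per minute. With no sleep rule, the two-hour zero exclusion is the only thing that can take sleep out, and it was written to detect a monitor that is not worn. It removes a night with the monitor off, because that night is one long run of zeros. It removes worn sleep only where zeros run unbroken for two hours. One minute with a small movement ends the run.

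Measured sedentary time therefore depends partly on whether the participant slept in the belt and how movements were spread through the night. Neither is the behaviour the programme targets. At stake are the level and precision of a secondary behavioural measure. There is also a decision left open: without a stated rule, whoever processes the data must choose how to treat nights, possibly after seeing results.

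**Working it through.** The plan states no figure on this point, so there is nothing to reproduce. The check applies the written rule minute by minute to one night.

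**Inputs from the protocol.** A reading below 100 counts per minute is sedentary. A run of 120 or more consecutive zero minutes is excluded.

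**Assumptions (the documents give no values).** The night lasts 8 hours, or 480 minutes. A share p of minutes has a small movement, non-zero but below 100 counts. These minutes occur either singly and independently, or in 5-minute bouts.

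**Formula.** Minutes scored sedentary = moving minutes + all zero minutes in runs shorter than 120.

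**Check by hand.** Take four moving minutes in the night (4/480 = 0.83%).
- Evenly spaced, they leave 476 zero minutes in five runs averaging 476/5 = 95.2 minutes. No run reaches 120, so all 480 minutes are scored sedentary.
- Placed together in the middle, they leave two runs of 238 minutes. Both are excluded, so 4 minutes are scored sedentary.
- With no moving minutes, or with the monitor off, there is one run of 480 and the score is 0.

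**Simulation of the same rule (mean minutes scored sedentary per worn night).**

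| Share of minutes moving | 5-minute bouts | Single minutes |
|---|---|---|
| 0 | 0 | 0 |
| 1% | about 40 | about 210 |
| 2% | about 80 | about 360 |
| 5% | about 220 | about 475 |

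At 0.5% with single minutes the mean is about 100. A night with the monitor off scores 0 in every row.

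**What this does to the outcome.** Let m be the minutes added per worn night and f the share of participants who always sleep in the monitor. Assume f = 0.5 and a between-person SD of waking sedentary time of 90 minutes (variance 8,100).
- Rise in the mean = f × m.
- Variance ratio = 1 + m² × f(1 − f)/8,100.
- Shift between arms if overnight wear differs by 10 percentage points = 0.10 × m.

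| m | Rise in mean (min/day) | Variance ratio | Shift for a 10-point difference (min/day) |
|---|---|---|---|
| 0 | 0 | 1.00 | 0 |
| 40 | 20 | 1 + 400/8,100 = 1.05 | 4 |
| 210 | 105 | 1 + 11,025/8,100 = 2.36 | 21 |
| 220 | 110 | 1 + 12,100/8,100 = 2.49 | 22 |
| 475 | 238 | 1 + 56,406/8,100 = 7.96 | 48 |

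The variance ratio treats night wear as a fixed habit and m as constant. If people vary from night to night, averaging over seven days reduces it. If the habit is stable, adjusting for the T1 value would remove much of it, but section D states baseline adjustment only for BMI.

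**The case against.** The strongest reply is that the protocol does not score every minute below 100 counts as sedentary. A reader who stops at the cut point might infer that it does, but the next sentence excludes long zero runs. That exclusion removes all overnight non-wear and part of worn sleep. This stands: hours of added sleep are possible, not certain, and a perfectly still night adds nothing.

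Second, the size rests entirely on assumptions. At the same 1% of moving minutes, the result falls from about 210 to about 40 minutes if movements cluster. This also stands, and it is why no single figure should be quoted.

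Third, the user manual or the written directions may tell participants to take the monitor off at night. They may, so the absence of a night-wear instruction can be claimed only for the visible text. Even so, an instruction would not settle how to score the nights of those who keep it on.

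Fourth, the reach is limited. BMI is the primary outcome, Aim 2 refers to physical activity behaviour, and no aim names sedentary time. This stands and keeps the point minor. Sedentary time is still a declared output of the monitor.

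**Conclusion.** The point holds as a cheap improvement. The written rule, followed exactly, puts an uncontrolled share of worn sleep into sedentary time. For an assumed 8-hour worn night that share runs from 0, through about 40 to 210 minutes with 1% of minutes moving, to about 220 to 475 minutes with 5% moving. Movement rate, clustering, night length, overnight-wear share and waking SD are all assumptions.

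The consequence is an inflated level and extra between-person noise. A reader might go further in three ways that the documents do not support:
- **That the comparison between arms is biased.** This needs overnight wear or sleep movement to differ by arm, and the documents give no evidence of that. With ten schools per condition, chance differences between schools need not average out, but this is a possibility, not a finding.
- **That a programme which improves sleep would appear to raise sedentary time.** Longer worn sleep broken by movement could add minutes. Stiller sleep lengthens the zero runs, which are excluded, so it would lower the figure.
- **That the main results are at risk.** BMI and its power calculation do not use these data, and sleep minutes below 100 counts never enter moderate or vigorous minutes.

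**What to change.** Add to the Daily Physical Activity paragraph that sedentary time is counted only in waking hours. The sleep period should be removed by one pre-specified rule, either a sleep-detection algorithm on the minute counts or a single fixed clock window. This should happen before the 100-count cut point and the two-hour zero rule are applied, identically in both arms and at T1, T2 and T3. The rule should say that a zero run crossing the edge of the sleep period is judged on its full length. Otherwise a belt taken off shortly before the window opens could leave a remainder of under two hours that is scored as sedentary. If the manual or the written directions already contain a night-wear instruction, the protocol should cite it.

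The cost is one processing step on data already downloaded, with no new measurement. Sleep then adds nothing to sedentary time whether or not the monitor is worn at night, apart from errors in placing the sleep period. The downside is small: some late-evening or early-morning waking minutes will be misclassified.

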### **Psychosocial Determinants**

**Outcome Expectations for Physical Activity:** The outcome expectancy values instrument in this study assesses outcome expectations and their associated expectancies for physical exercise by requesting information on six dimensions: relaxation, fitness, competition, social growth, social continuation, and health. Each of the eight dimensions is measured by five items. Previous studies demonstrated internal consistency, reliability coefficient ranging  $\alpha = 0.86-0.97$  when used with Appalachian teens. Construct validity has also been demonstrated through three confirmatory factor analyses using data from our previous work.

**Self-Efficacy for Physical Activity:** Self-efficacy will be measured using a previously developed instrument with 14 items. The instrument has demonstrated predictive validity for boys and girls: 0.23 and 0.27 Re-test reliability of this scale has been reported to be 0.82. This instrument has been refined by adding three additional items and altering the response scale from dichotomous to a five-point Likert-type scale, with internal reliability consistency ranging  $\alpha = .85-.94$ .

### **Self-Regulation**

**Self-regulation for Physical Activity Questionnaire** contains six subscales: Behavioral Goal Setting, Self-Monitoring, Overcoming Barriers, Time Management, Self-Reward, and Planned Social Support. The

instrument was developed by Co-PI [name] using a three-stage expert panel review to establish content validity. Internal reliability ranged from 0.89 to 0.95. Construct validity has been demonstrated through confirmatory factor analyses.

**Social Support:** Social support is measured using a self-report questionnaire containing 13 items originally developed by Reynolds et al. and refined by Trost et al. This instrument measures instrumental social support, social encouragement, and social expectations that are provided by friends and family members for physical exercise. In order to increase the internal reliability of the instrument, the original reporting scale was expanded to a five-point Likert-type scale. This instrument has previously been demonstrated to have construct validity. Internal reliability ranged  $\alpha = .75\text{-.88}$ , and re-test reliability ranged  $R = 0.78\text{-.93}$ .

### **Environmental Determinants**

**Perceived Environment for Physical Activity:** Perceived environment is measured by one Likert scale. The 8-item subscale focuses on the perceived neighborhood environment. Construct validity and test-retest reliability have been established for this scale when used with adolescents residing in rural communities.

### **Acceptability, Ease of Delivery, and Usefulness of Curricula Delivery Approach**

**Cognitive Interviews:** Semi-structured interviews will be conducted on a randomly selected subset of mentor and teacher participants. Questions focus on acceptability, ease of delivery, and usefulness of curriculum.

## **B. Detailed Study Procedures**

Anthropometric and other quantitative data will be in a designated private room at each participating high school at all data-collection time-points ( $T_1$ ,  $T_2$ , and  $T_3$ ). Questions will be read aloud to accommodate any reading difficulties and be available to answer questions. Prior to baseline data collection, a series of training sessions will be held to train data collection staff responsible for taking measurements, including physical activity using Actical accelerometers (Actical, Bio-Lynx Scientific Equipment, Montreal), BMI, body fat, and administration of the data collection instruments. The measurement team training will held at the Project Office located on the OSU campus. In order to assure standardization and quality of data collection, this training will include a review of the eligibility criteria and consent procedures; overview of the measurement protocol; demonstration of the measurement methods; and an opportunity to have each measurement team mock data collect on several subjects and gain expert feedback on their ability to follow protocol. This training will occur prior to each data collection time period ( $T_1$ ,  $T_2$ , and  $T_3$ ). The accelerometer data collection training will be done by [name]. [name] is an expert in accelerometer use and accelerometer data processing. Body fat analysis measurement training will be conducted by [name] an advanced practice registered nurse and expert in the collection of anthropometric data in community settings. The survey data collection training will be conducted by [name] and [name]. The Project Office will ensure that the measurement teams perform only those functions for which they are certified, and that re-certification activities are implemented as planned in a timely manner.

Participants will receive \$15 at each data-collection time-point. Anthropometric measures (height, weight, and body fat) will be collected from each privately. BMI will be calculated by: weight (lb)/[height (in)]  $\times 703$  (Measures). Pilot testing found anthropometric data collection will take 10-15 minutes. BMI percentiles for children will be calculated via computer using CDC guidelines. Data from peer mentors will be collected by an RA at completion of mentor training ( $T_1$ ), at the end of the academic year ( $T_2$ ), and beginning of the following academic year ( $T_3$ ). See Table 5 (next page) for the data collection plan and process.

In adherence to school and district policies, teacher participants will not be provided any financial incentive for their participation.

Informed consent will be documented on a participant tracking form. This form allows linkage of the participant to their study identification number. For subsequent data collection, the identification number will be used instead of any identifiable information. All databases will be encrypted and password-protected. We will use a registration and tracking number that is randomly generated to document all measurement activities within individuals. Once informed consent is given, information on physical activity levels will be collected using the Actical accelerometer. Collection of the physical activity variable requires that the Actical be worn by the study participant for seven study days, and requires two school visits by the measurement team for each participant. Participants will be informed of the procedure used to wear the Actical monitor as outlined in the Actical user manual. There will be a demonstration of the correct right iliac crest placement of the monitor using a belt provided by the study. Each subject will receive a belt that allows for the correct placement of the monitor and written directions for the subject and parent to assure correct placement of the device in subsequent days. The subject will receive a reminder daily from their classroom teacher during the monitoring period to make sure that they are wearing the monitor and to answer any questions they may have. After seven days of monitoring, the measurement team will return to the school collect the devices, debrief the participant, and provide an incentive. Actical monitor data will be downloaded to a laptop PC at the school site by the measurement team. This requires the use of the download device and software provided by the vendor. The monitor will then be reset and redistributed for use by another

subject in that school. This process will be repeated weekly for three weeks at each school, representing three waves of data collection in a different one-third of the participating students each week.

One week prior to implementation of the intervention, a measurement team will go to the school for another data collection day that involves survey instrument and data collection. Each data measurement team will read explicit directions regarding how the survey will be filled out. With each instrument the measurement team will read the directions, answer questions, and then allow the students to fill out each instrument. When the entire battery is completed, the measurement team will collect the data, count the surveys, and record the count on a data sheet that is placed in a box and sealed. This box will not be opened until it reaches the project office to be counted to verify there are no missing forms.

The questionnaire will administered in a group setting each day for a week at the beginning of the health class period using a paper-and-pencil format. Filling out the survey takes approximately 10 minutes, and each day it gets easier and faster to fill out as the students become accustomed to it. On Friday, the students are given two questionnaires to be filled out as homework each night before bed and to be signed by a parent as completed on that date. This will provide for a seven-day total of activities the student recalls. Again, when the entire group of questionnaires is completed, the measurement team will collect the data, count the surveys, and record the count on a data sheet that is placed in a box and sealed. This box will not be opened until it reaches the project office to be counted to verify there are no missing forms. Questionnaires and data forms will be kept in a locked cabinet in the project office. Demographic information or identifiable data will be removed immediately from the questionnaire, transported, and stored separately from the questionnaire.

**Table 5: Data Procedures and Process**

Time	Process:	(Data Provided By)	Team Member
YEAR 1			
	Finalization of data collection protocols Finalization of participating schools to Waves 1 or 2 Training of PD and RAs: protocols, use of accelerometers Randomization of Wave 1 schools to either intervention or comparison	[name] & [name] [name] & [name] [name] & [name] ([name])	
WAVES 1,2			
Consent	Consent/Accent of Peer Mentors and School Participants	[name] or [name]	
End of Recruitment	1. Assignment of identification numbers to subjects, mentors, and teachers 2. Demographic Questionnaire (Peer Mentor, Subjects)	[name] Team	
Baseline (T 1 )	Subject Survey Questionnaire: Self-Report Height, weight, BEI Accelerometer – one week of data a Health Behaviors Questionnaire: (Subjects) (Subjects) (Teachers, Peer Mentors, Subjects) (Peer Mentors, Subjects)	Team	
T 1 : Follow-Up	Collection of accelerometer data (7 days)	Team	
Weekly	Debriefing sessions: observations and notations: mentors and teachers Measures of Fidelity (mentors and teachers) Data Interim Reports	[name] & [name]	
Monthly	Measures of Fidelity (mentors and Teachers)	[name] & [name]	
3 Months Post Intervention (T 2 )	Subject Survey Questionnaire: Self-Report Height, weight, BEI Accelerometer – one week of data a Health Behaviors Questionnaire (Subjects) (Subjects) (Teachers, Peer Mentors, Subjects) (Peer Mentors, Subjects)	Team	
T 2 : Follow-Up	Collection of accelerometer data (7 days) Reinforcement (Booster) Session	Team	
6 Months Post Intervention (T 3 )	Survey Questionnaire: Self-Report Accelerometer – one week of data a Health Behaviors Questionnaire (Subjects) (Teachers, Peer Mentors, Subjects) (Peer Mentors, Subjects)	RA (blinded to group)	
T 3 : Follow-Up	Collection of accelerometer data	Team	

BEI = bio-electronic impedance; aAccelerometer data collected over 3 weeks (1/3 of subjects each week to wear for 1 week)

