In academic underperforming schools such as those prevalent in Appalachia, the primary educational focus is to meet core academic mandates. To meet academic mandates, despite school-based health education and physical education programs, most Appalachian schools no longer require health and physical education. Low rates of physical activity and high rates of obesity persist in Appalachia. Efforts to improve physical activity in school-aged adolescents residing in Appalachia have relied on organized sports and school-based curricula delivered by teachers. These approaches have not been effective for Appalachian teens. One explanation may be **unique circumstances** present within Appalachia. Opportunities to participate in organized sports are limited due to inadequate school resources, lack of available transportation, and limited availability of school teams. As a result, most adolescents residing in Appalachia are unable to participate in organized sports. Further, school-based health interventions are limited in their scope and impact on obesity prevention. School-based interventions typically deliver content as part of a regular course such as health or physical education via teachers in classroom settings (this is the proposed comparison intervention). Low efficacy of these programs may be due to unique cultural challenges: a preference for informal sharing of information among local residents rather than health content delivered by formal teachers. Rarely do adolescent obesity prevention programs use peer mentoring. Though school-based interventions increase health knowledge, there is less evidence of the effectiveness for health behavior changes leading to **obesity prevention**. Longer-term follow-up of health behavior and health status outcomes in intervention studies are lacking.

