#### **Rationale**

*Planning to be Active* (PBA) is a theory-based program for promoting regular physical activity in high school teens in Appalachia. In pilot studies, PBA was delivered by classroom teachers and showed efficacy in producing short-term increases in physical activity. Additionally, the research team has developed and tested a peer mentoring program based upon similar theoretical constructs used in PBA to successfully promote daily physical activity changes in Appalachian youth. Building upon these successes and our experience in this highly vulnerable population, we propose to expand the PBA intervention to be delivered in an after school program by trained high school mentors from Appalachia. We predict that peer mentors will be more effective than classroom teachers and will improve their own health behaviors, providing a double-edged intervention. Employing high school mentors as agents of change further addresses a unique need of Appalachian residents who often lack access to or trust in health professionals.

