#### **Sample**

We conducted a careful analysis of sample size calculations for primary analysis of the primary outcome: BMI in adolescents at 6 months post intervention. As discussed further below, we will use a mixed model ANCOVA in our primary analysis. Power calculations for this approach are given by Murray. Power in a G-RCT is influenced by five factors: number of groups (schools), number of individuals in each group (adolescents in each school), similarity of outcomes within clusters (school-level intra-class correlation [ICC] for BMI), similarity of outcomes within individuals (correlation of BMI measurements on the same student over time), and percentage of the variance that can be explained by the regression model. Using data from the **Ohio Family Health Survey**, we estimate that the school-level ICC for BMI among 9th graders in Appalachian Ohio counties is 0.023. We further estimate the over-time correlation of BMI measurements is 0.70 and that adjusting for age and gender will explain approximately 30% of the variance in BMI. With these assumptions, 10 schools per condition, and 75 students per school, we will have 82% power to detect a modest intervention effect (0.2 standard deviation difference between groups). This effect size would correspond to a difference in mean BMI between groups of 1.04 kg/m^2 if the observed variation in BMI is similar to that of all Appalachian 9th graders from the Ohio Family Health Survey (mean BMI = 23.41, SD = 5.2).

With an average of 75 mentee participants per school (50% participation rate of eligible students based on our preliminary work), we estimate that a total of 1,500 9th and 10th grade participants will be recruited over 2 years (750 per year). Further, 190 older teens will be recruited to serve as peer mentors (19 per school x 10 schools) in the MBA condition, for a study total of 1,690 high school-aged children. Recruitment of mentor and mentee participants will occur during the start of the school year (September).

At the end of the academic year, we will randomly select at least 1 PBA teacher and 5 teen mentors from each school that delivered the curriculum that year to participate in cognitive interviews. These semi-structured interviews will be conducted individually and will be audio-recorded. Audio recordings will be transcribed verbatim. Each interview will last approximately 30 minutes and will be held in a private room at each school.

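### Wave 1 schools are randomised before students consent and the arm is probably visible at recruitment, so balance is not assured among the students who volunteer

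*Combined protocol and SAP*

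**What the plan says.** Table 5 (Data Procedures and Process) has a Year 1 block that ends with "Randomization of Wave 1 schools to either intervention or comparison". The block for Waves 1 and 2 follows, opening with "Consent/Accent of Peer Mentors and School Participants", then end of recruitment, then baseline (T1). The table has no calendar dates, and it does not say when Wave 2 schools are randomised. The one statement on blinding is at T3, where the team member is given as "RA (blinded to group"; the consent and T1 rows carry none.

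The Sample section fixes the recruitment window: "Recruitment of mentor and mentee participants will occur during the start of the school year (September". It also says that "190 older teens will be recruited to serve as peer mentors (19 per school x 10 schools) in the MBA condition", and it plans 75 mentees per school on a "50% participation rate of eligible students based on our preliminary work". The Rationale describes the new format as a plan to "expand the PBA intervention to be delivered in an after school program by trained high school mentors from Appalachia"; Participant Recruitment and Retention has school health teachers deliver the comparison in classrooms.

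Section C (Internal Validity) rests equivalence at pretest on randomisation of schools and commits to intention-to-treat. Section D (Data Analysis) adjusts the primary comparison for baseline BMI.

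**The concern.** In a group-randomised trial, random assignment makes the schools, and the eligible students in them, comparable in expectation. It does the same for enrolled students only if the decision to enrol cannot depend on the arm. Here, recruiting mentors at a school in September would itself signal that the school is in MBA. An after-school programme led by older peers may attract different students from a teacher-led class; the Background even names "lack of available transportation" as a local obstacle, though for organised sports.

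If volunteering depends on the arm, part of any difference between arms reflects who joined. Intention-to-treat starts from the enrolled students, so it comes too late to help. Multiple imputation has the same starting point. Adjustment for baseline BMI, and for the demographic and psychosocial measures taken before the intervention, reduces the problem but leaves whatever is due to unmeasured traits such as motivation.

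**Working it through.** **Sequence.** Four statements, set side by side: Wave 1 schools are randomised in the block before consent (Table 5); mentors are needed in MBA schools only (Sample); mentors and mentees are recruited in the same month (Sample); mentors attend the same school as their mentees (Participant Recruitment and Retention). If mentors are recruited only where MBA has been allocated, the allocation has to be known to someone at the school while mentees are being approached. That it reaches the students is likely but not stated.

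**Scope for selection.** 75 enrolled at 50% participation implies 75 / 0.50 = 150 eligible per school, so about 75 per school do not enrol.

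**Precision.** Inputs from Sample and Participant Recruitment and Retention: 10 schools per condition, 75 students per school, ICC 0.023, over-time correlation 0.70, 30% of variance explained by age and gender, effect 0.20 SD, BMI SD 5.2, power 82% (82.5% with 80% retention). The significance level is not stated; I assume two-sided 5%, with 2 x (10 - 1) = 18 df.

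- Variance of the difference = 2[(1 - ICC) x a + m x ICC x b] / (m x 10), where m is students per school and a and b are the shares of student-level and school-level variance left after adjustment. The documents do not give a and b.
- With a = (1 - 0.70²) x (1 - 0.30) = 0.357 and b = 0.70, power is about 83.5% at m = 75 and 81.5% at m = 60. The stated figures are reproduced to within about 2 points.
- To avoid choosing a split, I take the standard error that the stated power implies (noncentral t): 0.0658 SD for 82%, 0.0653 SD for 82.5%.

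**Illustrative bias on BMI.** Assumptions, none of them from the documents: a standard normal unmeasured trait shifts enrolment odds by a factor of 1.1 to 1.5 per SD in one arm only, and its partial correlation (r) with follow-up BMI given baseline is 0.1 to 0.2.

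- Trait difference between arms at 50% participation (logistic enrolment): 0.048 SD at odds ratio 1.1; 0.195 SD at 1.5.
- Bias = trait difference x r x residual SD, with residual SD = sqrt(1 - 0.70²) = 0.714.
- Low end: 0.048 x 0.1 x 0.714 = 0.0034 SD, or 0.02 kg/m². High end: 0.195 x 0.2 x 0.714 = 0.0279 SD, or 0.14 kg/m².
- Type I error: 5.0% at the low end, 6.9% at the high end.
- If the 30% for age and gender applies on top of baseline BMI, residual SD = sqrt(0.51 x 0.70) = 0.597. The high end becomes 0.195 x 0.2 x 0.597 = 0.023 SD, with type I error about 6.3%.

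**What a material bias would need.** Take 0.05 SD (0.05 x 5.2 = 0.26 kg/m²; type I error about 11%), with residual SD 0.714.

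- r = 0.2: trait difference 0.05 / (0.2 x 0.714) = 0.35 SD, an enrolment odds ratio of about 2.2 per SD.
- r = 0.1: 0.05 / (0.1 x 0.714) = 0.70 SD, an odds ratio of about 25.
- With residual SD 0.597, r = 0.2 needs 0.42 SD (odds ratio about 2.8). r = 0.1 needs 0.84 SD, above the maximum of about 0.80 SD that this one-arm model allows.

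**Physical activity.** No ICC or over-time correlation is given, so no comparable calculation is possible.

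**Power cost of concealed consent.** If a share f of MBA enrolees cannot attend and gets no benefit, the effect is 0.20 x (1 - f). For f = 5%, 10% and 20% it is 0.19, 0.18 and 0.16 SD, and power falls from 82% to about 78%, 74% and 63%.

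**The case against.** Three objections carry weight. First, what students are told belongs naturally in consent and recruitment material, which was not available, and Table 5 has no dates. A reader might infer that the plan has no concealment, or that Wave 2 follows the same order as Wave 1. The documents support neither: they are silent on disclosure in the pages available, and on Wave 2 timing altogether.

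Second, the effect on the primary outcome looks small. A reader might infer that recruitment after randomisation has biased the BMI comparison, or will do so materially. The figures do not show that. Every odds ratio and correlation is assumed, and a 0.05 SD bias needs strong selection in one arm at r = 0.2 and implausibly strong selection at r = 0.1.

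Third, the remedy has its own costs. Students who consent without knowing the arm may be unable to stay after school, and the power lost could outweigh the illustrated rise in type I error on BMI. Limiting enrolment to students who could attend either format would narrow the population and would also require a place in the health classes. Section B takes mentor T1 data at completion of mentor training, so later mentor training delays mentor T1.

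These points limit the size of the concern and make some remedies optional. They do not answer the design point: the stated order leaves room for selection that the analysis cannot fully undo, and the expectation in Section C does not extend to students who enrol with the arm in view.

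**Conclusion.** The point holds as a risk to be removed, not as bias shown. It rests on the row order of Table 5 for Wave 1 and on the inference that MBA-only mentor recruitment in September makes the arm visible to mentees. Confidence is medium, because consent and recruitment material could change that inference.

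For BMI, under the assumed inputs, the consequence is probably small. The more serious exposure is Aim 2, which compares the arms on physical activity: motivation to volunteer is a plausible confounder there, and the documents give nothing with which to bound it. Because the change is one of sequence and needs no new participants or measurements, it is worth making even though the BMI effect is likely to be minor.

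**What to change.** 1. In Table 5, for each wave including Wave 2, either randomise schools or disclose the allocation only after mentee consent has closed in all schools of that wave. Where the calendar allows, hold disclosure until T1 height and weight have been taken. At the 10 to 15 minutes per student given in Section B, anthropometry for 75 students takes 12.5 to 18.75 station-hours per school.
2. Use the same invitation, describing both formats, in every school.
3. Recruit and train MBA mentors after disclosure.
4. Where Wave 1 cannot be re-sequenced, apply this to Wave 2, and report eligible, approached and enrolled numbers and baseline characteristics by arm.

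The costs are a short delay to programme start and to mentor T1, and the loss of power shown above if some MBA enrolees cannot stay after school. Those students remain in the intention-to-treat analysis.

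Two additions are optional. Enrolling only students able to attend either format limits that dilution; if it removes 10% of enrolees in both arms (75 to 67.5 per school), power falls from 82% to about 80%, and the population is narrower. Taking mentor applications in all schools before disclosure would shorten the delay, but applicants in the 10 comparison schools (about 190 if 19 apply in each) would not serve.
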